## 5.2.2 Exclusion Criteria

Subjects will be excluded if they meet any of the following exclusion criteria at the specified assessment time points:

<Regarding medical history and complications>

- 1) Patients with a concurrent mental disorder besides schizophrenia who are judged by the investigator to be unsuitable for participation in the trial
- 2) Patients who have met the DSM-5® diagnostic criteria for substance-related or addictive disorder, including alcohol and benzodiazepines but excluding caffeine and tobacco, within 180 days before commencement of IMP administration
- 3) Patients with a positive drug test at screening

However, patients who tested positive for a drug other than cocaine may be included if their condition is not diagnosed as any substance-related or addictive disorder, according to the DSM-5® diagnostic criteria.

- 4) Patients who fall under any of the following criteria regarding suicidal ideation and suicidal behavior
  - Patients who answered “yes” to Question 4 “Active Suicidal Ideation with Some Intent to Act, without Specific Plan” or Question 5 “Active Suicidal Ideation with Specific Plan and Intent” regarding C-SSRS suicidal ideation at screening (for the past 6 months) or at the Period 1 baseline examination (since the last assessment)
  - Patients who exhibited suicidal behavior on C-SSRS at screening (for the past 2 years) or at the Period 1 baseline examination (since the last assessment)
  - Patients who present a serious risk of suicide based on the judgment of the investigator
- 5) Patients who have previously undergone gastrointestinal surgery that could affect PK evaluation
- 6) Patients who have undergone major surgery or blood transfusion or who have made a blood donation (whole blood or blood plasma) within 30 days before the acquisition of informed consent
- 7) Patients who have a clinically significant neurological, hepatic, renal, metabolic, hematological, immunological, cardiovascular, pulmonary, or gastrointestinal disorder.  
Medical conditions that are minor or well-controlled may be considered acceptable if the condition does not interfere with safety and PK assessments.
- 8) Patients with any of the following laboratory or ECG values at screening (according to the results from the central laboratory or the central ECG laboratory)

Platelets:  $\leq 75000/\text{mm}^3(\mu\text{L})$

Hemoglobin:  $\leq 9 \text{ g/dL}$

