Neutrophils, absolute: $\leq 1000/\text{mm}^3$	Aspartate aminotransferase (AST): $> 2 \times$ upper limit of normal (ULN)
Alanine aminotransferase (ALT): $> 2 \times$ ULN	CPK: $> 3 \times$ ULN
Creatinine: $\geq 2 \text{ mg/dL}$	QT interval corrected for heart rate using Fridericia's formula (QTcF): $> 450$ milliseconds
9) Patients who fall under any of the following criteria at screening	
• Inadequately controlled hypertension (supine or sitting diastolic blood pressure of $> 95 \text{ mmHg}$ )	
• Symptomatic hypotension	
• Orthostatic hypotension, defined as a decrease of $\geq 30 \text{ mmHg}$ in systolic blood pressure or a decrease of $\geq 20 \text{ mmHg}$ in diastolic blood pressure after standing for at least 3 minutes compared with the supine values prior to standing	
10) Patients meeting any of the following criteria	
• Patients with type 1 diabetes mellitus or patients with type 2 diabetes mellitus being treated with insulin	
• Patients with type 2 diabetes mellitus who have not been maintained on a stable regimen of anti-diabetic medication(s) or undergone diet/exercise therapy for at least 28 days prior to screening	
• Patients meeting either of the following criteria for poor blood glucose control at screening	
– Glycosylated hemoglobin (HbA1c) of $\geq 7.0\%$ according to the global standard value	
– fasting blood glucose level of $\geq 126 \text{ mg/dL}$ or nonfasting blood glucose level of $\geq 200 \text{ mg/dL}$	
11) Patients with a complication of hypothyroidism or hyperthyroidism (except in cases where the condition has been kept stable for at least 90 days at the time of screening through drug therapy) or patients who show abnormal values for thyroid-stimulating hormone (TSH) and free thyroxin (FT4) at screening	
12) Patients with a complication of ischemic heart disease, myocardial infarction, or congestive heart failure (whether controlled or uncontrolled), or with a history of angioplasty, stenting, or coronary artery bypass surgery	
13) Patients with a history or complication of epilepsy or seizures, except for childhood febrile seizures, post-traumatic seizures, alcohol withdrawal seizures, etc	
14) Patients with a history or a complication of neuroleptic malignant syndrome	
15) Patients with a history or a complication of paralytic ileus	
16) Patients with a history or a complication of water intoxication	
17) Patients with a history or a complication of rhabdomyolysis	

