### **9.3 Clinical Laboratory Data**

For each quantitative laboratory parameter, descriptive statistics of actual measurements and changes from baseline at each time point will be calculated.

For each quantitative laboratory parameter, measured values will be classified as “lower than the lower limit of the reference range,” “within the reference range,” and “higher than the upper limit of the reference range” using the reference ranges specified by the central laboratory, and a shift table from baseline in each period will be produced.

For each qualitative laboratory parameter, a shift table from baseline in each period will be produced.

The number and proportion of subjects in whom any measurement after IMP administration in each period up to before IMP administration in the next period (if the IMP is to be administered in the next period) meets the criteria for potentially clinically significant laboratory test values (Appendix 1) will be determined. A listing of subjects who meet the criteria will be provided.

The number and proportion of subjects in whom alanine aminotransferase (ALT), aspartate aminotransferase (AST), and total bilirubin (TBL) after IMP administration in each period up to before IMP administration in the next period (if the IMP is to be administered in the next period) meet Hy’s Law criteria ( $ALT \text{ or } AST \geq 3 \times \text{upper limit of normal [ULN]}$  and  $TBL \geq 2 \times \text{ULN}$ ) will be determined. A listing of subjects who meet the criteria will be provided.

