## Appendix 1 Criteria for Identifying Laboratory Values of Potential Clinical Relevance

Laboratory Tests	Criteria
Chemistry	
AST (SGOT)	$\geq 3 \times$ upper limit of normal (ULN)
ALT (SGPT)	$\geq 3 \times$ ULN
Alkaline phosphatase	$\geq 3 \times$ ULN
LDH	$\geq 3 \times$ ULN
BUN	$\geq 30$ mg/dL
Creatinine	$\geq 2.0$ mg/dL
Uric Acid	
Men	$\geq 10.5$ mg/dL
Women	$\geq 8.5$ mg/dL
Bilirubin (total)	$\geq 2.0$ mg/dL
CPK	$\geq 3 \times$ ULN
Prolactin	$>$ ULN
Hematology	
Hematocrit	
Men	$\leq 37\%$ and decrease of $\geq 3$ percentage points from Baseline
Women	$\leq 32\%$ and decrease of $\geq 3$ percentage points from Baseline
Hemoglobin	
Men	$\leq 11.5$ g/dL
Women	$\leq 9.5$ g/dL
White blood count	$\leq 2,800/\text{mm}^3$ or $\geq 16,000/\text{mm}^3$
Eosinophils	$\geq 10\%$
Neutrophils	$\leq 15\%$
Absolute neutrophil count	$\leq 1,000/\text{mm}^3$
Platelet count	$\leq 75,000/\text{mm}^3$ or $\geq 700,000/\text{mm}^3$
Additional Criteria	
Chloride	$\leq 90$ mEq/L or $\geq 118$ mEq/L
Potassium	$\leq 2.5$ mEq/L or $\geq 6.5$ mEq/L
Sodium	$\leq 126$ mEq/L or $\geq 156$ mEq/L
Calcium	$\leq 8.2$ mg/dL or $\geq 12$ mg/dL
Glucose	
Fasting	$\geq 100$ mg/dL
Non-Fasting	$\geq 200$ mg/dL
Total Cholesterol, Fasting	$\geq 240$ mg/dL
Triglycerides, Fasting	$\geq 150$ mg/dL

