## Appendix 2 Criteria for Identifying Vital Signs and Weight of Potential Clinical Relevance

Variable	Criterion Value a	Change Relative to Baseline a
Pulse Rate	> 120 bpm < 50 bpm	$\geq 15$ bpm increase $\geq 15$ bpm decrease
Systolic Blood Pressure	> 180 mmHg < 90 mmHg	$\geq 20$ mmHg increase $\geq 20$ mmHg decrease
Diastolic Blood Pressure	> 105 mmHg < 50 mmHg	$\geq 15$ mmHg increase $\geq 15$ mmHg decrease
Weight	-	$\geq 7\%$ increase $\geq 7\%$ decrease

aIn order to be identified as potentially clinically relevant, an on-treatment value must meet the “Criterion Value” and also represent a change from the subject’s baseline value of at least the magnitude shown in the “Change Relative to Baseline” column.

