**Appendix 3 Criteria for Identifying ECG Measurements of Potential Clinical Relevance**

Variable	Criterion Valuea	Change Relative to Baselinea
Heart Rate	$\geq 120$ bpm $\leq 50$ bpm	increase of $\geq 15$ bpm decrease of $\geq 15$ bpm
PR	$\geq 200$ msec	increase of $\geq 50$ msec
QRS	$\geq 120$ msec	increase of $\geq 20$ msec
QTcF	$> 450$ msec (males and females)	

aIn order to be identified as potentially clinically relevant, an on-treatment value must meet the “Criterion Value” and also represent a change from the subject’s baseline value of at least the magnitude shown in the “Change Relative to Baseline” column.

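### The laboratory PCS table counts any post-dose value whatever the period baseline, so CT-10.4.1 mixes pre-existing with new abnormalities; apart from prolactin, no planned summary table is defined to count the new ones

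*SAP*

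**What the plan says.** SAP 9.3 defines the laboratory PCS count as the number and proportion of "subjects in whom any measurement after IMP administration in each period", up to the next period's dose, meets Appendix 1. Protocol 9.4.2.2 has the same rule. SAP 9 defines a baseline for each period (the last value before that period's dose), but the PCS rule does not use it. The only reference to baseline in Appendix 1 is for hematocrit, which needs a low value plus a fall of at least 3 "percentage points from Baseline". The other criteria, such as "Triglycerides, Fasting" at or above 150 mg/dL, are plain thresholds.

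The result appears in CT-10.4.1, titled as an incidence table, with a listing in CT-10.4.2. SAP 3.4 adds withdrawal and unscheduled values to this count.

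Entry limits are in protocol 5.2.2. Criterion 8 excludes "Patients with any of the following laboratory or ECG values at screening" beyond stated cuts. Criterion 10 excludes a "fasting blood glucose level of" 126 mg/dL or more. Criterion 7 is a matter of judgment: "Medical conditions that are minor or well-controlled may be considered acceptable" if they do not interfere with the safety and PK assessments.

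**The concern.** Confirming safety is the secondary objective, and laboratory tests are a listed safety endpoint. Every subject receives the drug under both meal conditions and there is no untreated arm, so the period baseline is the only internal reference for what changed after dosing. A rule that ignores it puts two kinds of subject in one count: those already beyond the cut before the dose, and those who crossed it afterwards. A reader of CT-10.4.1 cannot tell how many belong to each, although the second kind is what a post-dose incidence is usually taken to mean. What is at stake is the reading of one descriptive safety table.

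**Working it through.** The plan gives no PCS rate, so there is no figure of its own to reproduce. The check compares the texts and then scales the effect under stated assumptions.

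**1. How many criteria use baseline (SAP Appendix 1).** Chemistry 10 + hematology 7 + additional 7 = 24 analytes. One, hematocrit, refers to baseline. That clause does not isolate new crossings: a man at 36% before dosing who falls to 33% is counted (at or below 37%, fall of 3 points), although 36% was already at or below 37%.

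**2. Entry limits (protocol 5.2.2, criteria 8 and 10) against PCS cuts.**

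| Analyte | Excluded at screening | PCS | Allowed at entry and PCS |
|---|---|---|---|
| Fasting glucose, mg/dL | ≥126 | ≥100 | 100 to <126 (126 − 100 = 26 wide) |
| Hemoglobin, men, g/dL | ≤9 | ≤11.5 | >9 to 11.5 (2.5 wide) |
| Hemoglobin, women, g/dL | ≤9 | ≤9.5 | >9 to 9.5 (0.5 wide) |
| Platelets, high, per mm³ | no upper limit | ≥700,000 | ≥700,000 |
| CPK | >3 × ULN | ≥3 × ULN | exactly 3 × ULN |
| AST, ALT | >2 × ULN | ≥3 × ULN | none |
| Creatinine, mg/dL | ≥2 | ≥2.0 | none |
| Absolute neutrophils, per mm³ | ≤1,000 | ≤1,000 | none |
| Platelets, low, per mm³ | ≤75,000 | ≤75,000 | none |
| Non-fasting glucose, mg/dL | ≥200 | ≥200 | none |

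These rows cover 8 of the 24 analytes: platelets, hemoglobin, absolute neutrophils, AST, ALT, CPK, creatinine and glucose. The other 24 − 8 = 16, or 15 without hematocrit, have no visible numeric entry limit. They include triglycerides, total cholesterol and prolactin. Criterion 7, or the blacked-out criterion 28, may cover some of them. An entry of none refers to the screening value; it does not guarantee that a period baseline is clear, least of all in Period 2.

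**3. Do other planned summaries count new crossings?** The shift tables (CT-10.2.1 to CT-10.2.3) classify values against the central laboratory's reference range, from each period's baseline. For prolactin the PCS cut is above the ULN, which is the shift table's upper boundary, so movement into the high class in CT-10.2.1 does show new prolactin crossings at scheduled visits. It omits the withdrawal and unscheduled values that CT-10.4.1 uses. Another criterion would coincide only if its reference limit happened to equal its PCS cut, and the documents do not give those limits. CT-10.5.1 covers only the combined liver criterion.

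**4. The Period 2 pre-dose sample.** The counting window ends at the next dose, and protocol Table 1.3-1 schedules laboratory tests on Day −1 of Period 2. Read literally, that sample is both a Period 1 post-dose value and the Period 2 baseline. An abnormality arising after the first dose and persisting can therefore count under both meal conditions and also look pre-existing in Period 2.

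**5. Scale.** Take n = 36, the planned completers (SAP 3.1), all dosed under both conditions. One persistent case adds 1/36 = 2.8 percentage points to each column and 2.8 − 2.8 = 0 to the difference. An assumed 1 to 9 such subjects add 2.8 to 9/36 = 25.0 points to each column.

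To show the mixing, let p0 be the share meeting a criterion at period baseline, all persisting, and let q = 5% be the rate of new crossings among the rest. Both are assumptions. Expected count = 36 × [p0 + (1 − p0) × q].

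| p0 | Pre-existing | New | Table count | Share pre-existing |
|---|---|---|---|---|
| 0% | 0 | 1.8 | 1.8 | 0% |
| 10% | 3.6 | 32.4 × 0.05 = 1.6 | 5.2 | 69% |
| 20% | 7.2 | 28.8 × 0.05 = 1.4 | 8.6 | 83% |
| 40% | 14.4 | 21.6 × 0.05 = 1.1 | 15.5 | 93% |

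With q = 10% and p0 = 10%, the pre-existing share is 3.6/6.84 = 53%. The table count can rise steeply while the number of new cases falls slightly.

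**The case against.** The strongest reply is that protocol and SAP agree, that an any-post-dose count is a legitimate definition, and that the information is recoverable. With about 36 subjects, CT-10.4.2 together with LAB-1 and LAB-2 lets a reviewer separate persistent from new cases one by one. Fasting status is recorded (protocol 8.7.1.1). A laboratory value judged clinically significant becomes an adverse event, and adverse events are assessed against the subject's condition at the start of each period (protocol 8.8.1). All of this stands, and it is why the point is small. It does not supply the count: the listings require derivation by hand, and adverse event reporting depends on the investigator's judgment.

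A reader might infer that the laboratory rule is wrong because vital signs, weight and most ECG variables are handled differently. The footnote to Appendix 2 says "In order to be identified as potentially clinically relevant, an on-treatment value must meet the" criterion value and adds a minimum change; the table of "Criteria for Identifying ECG Measurements of Potential Clinical Relevance" carries the same footnote, with no change value for QTcF. That contrast does not support the remedy. Criterion plus change also counts subjects who were abnormal at baseline and worsened, and weight has no criterion value at all. A count of new crossings is a further definition, justified by what it tells the reader and not by uniformity.

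A reader might also infer from footnote h of protocol Table 1.3-1 that the screening sample will often serve as the Period 1 baseline. The documents limit this. The footnote needs dosing within 14 days of the screening examination, whereas the CYP2D6 sample must reach the laboratory at least 16 working days before dosing. The footnote can apply only if the screening laboratory tests are drawn later than that sample. The point does not depend on it.

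**Conclusion.** The concern holds as a limit on how CT-10.4.1 can be read. The laboratory PCS count ignores the period baseline for 23 of 24 analytes, the hematocrit clause does not isolate new crossings, and the entry criteria visibly admit some PCS-range values.

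Three stronger readings are not supported. First, it is not true that no summary table shows any new crossing, since the shift table does so for prolactin at scheduled visits. Second, the fed-fasting difference in counts is not biased by persistent cases in subjects dosed in both periods, because they add equally to both columns. Third, nothing here touches the primary PK analysis.

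The number of subjects affected cannot be derived. The percentages in the scale step rest on 36 subjects dosed twice, full persistence and invented rates, and only show how strongly the two kinds of case could mix. The entry-limit comparison rests on the visible exclusions. This is a worthwhile, inexpensive improvement to one descriptive safety output.

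**What to change.** Keep the planned count in CT-10.4.1. Add, for each meal condition, the number newly meeting each criterion among subjects whose period baseline (SAP 9) did not meet its threshold, hematocrit included. Show as not evaluable any subject whose baseline is missing or was taken in a different fasting status from the one the criterion specifies.

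For the added column, use the Period 2 pre-dose sample only as the Period 2 baseline. In CT-10.4.2, flag subjects who met a criterion at the Period 2 baseline but not at the Period 1 baseline, so that an abnormality arising after the first dose is not called pre-existing. Record the addition in SAP Section 15, which currently lists no changes.

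The cost is minor programming on data already collected, and a wider table. The added denominators can differ between meal conditions, so the new column is descriptive only. The planned and added counts also treat the Period 2 pre-dose sample differently, which needs a table footnote. The protocol-defined count does not change.

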### **9.4 Vital Sign Data**

For each vital sign parameter, descriptive statistics of actual measurements and changes from baseline at each time point will be calculated. Blood pressure and pulse rate measured in a sitting position will be used.

The number and proportion of subjects in whom any measurement after IMP administration in each period up to before IMP administration in the next period (if the IMP is to be administered in the next period) meets the criteria for potentially clinically significant vital signs (Appendix 2) will be determined. A listing of subjects who meet the criteria will be provided.

### **9.5 Physical Examination Data**

Listings of physical examination findings will be provided.

## **9.6      *Electrocardiogram Data***

For each ECG parameter, descriptive statistics of actual measurements and changes from baseline at each time point will be calculated.

A shift table from baseline for normal/abnormal judgment on ECG (judged by the investigator) in each period will be produced.

The numbers and proportions of subjects with actual measurements of QTcF interval of > 450 milliseconds, > 480 milliseconds, and > 500 milliseconds after IMP administration in each period up to before IMP administration in the next period (if the IMP is to be administered in the next period) will be determined. The numbers and proportions of subjects with changes from baseline of > 30 milliseconds and > 60 milliseconds will be determined.

The number and proportion of subjects in whom any measurement after IMP administration in each period up to before IMP administration in the next period (if the IMP is to be administered in the next period) meets the criteria for potentially clinically significant ECG values (Appendix 3) will be determined. A listing of subjects who meet the criteria will be provided.

## **9.7      *Other Safety Data***

### **9.7.1      *Body Weight and Body Mass Index***

For body weight and BMI, descriptive statistics of actual measurements and changes from baseline at each time point will be calculated.

The number and proportion of subjects in whom any measurement after IMP administration in each period up to before IMP administration in the next period (if the IMP is to be administered in the next period) meets the criteria for potentially clinically significant body weight (Appendix 2) will be determined. A listing of subjects who meet the criteria will be provided.

### **9.7.2      *Drug Induced Extrapyramidal Symptoms Scale***

For the DIEPSS total score (total of scores for items 1 through 8) and a score for each DIEPSS item, descriptive statistics of actual measurements and changes from baseline at each time point will be calculated.

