Predose	Blood sampling for plasma drug concentration measurement, physical examination, vital signs: within 2 hours predose Other: within 24 hours predose
3 hours postdose	±30 minutes
9 hours postdose	±30 minutes 12-lead ECG only: ±60 minutes
24, 36, 48, 72, and 120 hours postdose	±2 hours
168 hours postdose	±4 hours
240 and 312 hours postdose	±24 hours
Follow-up examination	+7 days at maximum

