### **6.5.2      Restricted Concomitant Medications or Therapies**

The use of the following medications is restricted from the day of IMP administration in Period 1 until completion of Day 14 examination in Period 2 or withdrawal examination, except for prohibited concomitant medications:

- Antipsychotics other than brexpiprazole  
The use of other antipsychotics at a steady dose and regimen is permitted. The dose or frequency may be reduced at the discretion of the investigator in response to symptom improvement or maintenance or from a safety perspective. As-needed use is not allowed.  
The upper limit of dose and regimen of antipsychotics are as follows:
  - Antipsychotic medication comprising no more than 2 active components, and
  - A daily dose equivalent to  $\leq 600$  mg/day of chlorpromazine
    - If multiple antipsychotics are taken in the same day, this is to be the combined equivalent dose.
    - Chlorpromazine equivalent doses are based on Equivalent Conversion Table for Antipsychotics, as specified separately.

However, this does not include administration of antipsychotic medication at doses equivalent to less than 100 mg/day of chlorpromazine, which are not expected to have any antipsychotic effect.

- **Antiparkinsonian drugs and valbenazine**

The use of these medications is permitted only when extrapyramidal symptoms are present and such use is necessary in the opinion of the investigator. The dose and regimen must comply with the instructions in the package insert, and dosing within 12 hours before Drug Induced Extrapyramidal Symptoms Scale (DIEPSS) assessment must be avoided. Prophylactic use is not allowed. Therefore, in subjects who are using antiparkinsonian drugs or valbenazine at the time of informed consent, even if they are without a history of extrapyramidal symptoms related to the concomitant medications, use of these medications must be suspended by the day of IMP administration.

Before new use or dose increase of such medications, extrapyramidal symptoms will be assessed by DIEPSS.

- **Beta-blockers**

The use of  $\beta$ -blockers will be permitted only for the treatment of nonpsychiatric complications (eg, cardiovascular disorders) and only if the dose and regimen remain unchanged from before participation in the trial.

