### 3.4 Trial Visit Window

Data at each time point will be summarized using data at the time point recorded in the case report form (these data will not be summarized at the time of withdrawal or follow-up examination). Unscheduled visit data will not be used. For the criteria of potentially clinically significant laboratory test values, vital signs, body weight, and ECG and the categorical analysis of QT interval as corrected by Fridericia's formula (QTcF) interval to be summarized at any time other than the time points, withdrawal and unscheduled visit data will also be used.

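### DIEPSS ratings required before an antiparkinsonian drug or valbenazine is started or increased are left out of the only DIEPSS summary unless they fall at a scheduled visit

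*SAP*

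**What the plan says.** **Protocol 6.5.2 (restricted medications)** covers antiparkinsonian drugs and valbenazine from Period 1 dosing to the end of the Period 2 Day 14 or withdrawal examination. "The use of these medications is permitted only when extrapyramidal symptoms are present and such use is necessary in the opinion of the investigator". It then requires an event-driven rating: "Before new use or dose increase of such medications, extrapyramidal symptoms will be assessed by DIEPSS". It also says that "dosing within 12 hours before Drug Induced Extrapyramidal Symptoms Scale (DIEPSS) assessment must be avoided".

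**SAP 9.7.2** covers the DIEPSS total (items 1 to 8) and each item: "descriptive statistics of actual measurements and changes from baseline at each time point will be calculated". Protocol 9.4.2.6.2 says the same. CT-14 in SAP Appendix 4 is the only DIEPSS table.

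**SAP 3.4** sets what counts as data at a time point. It uses the time point recorded in the case report form, and "these data will not be summarized at the time of withdrawal or follow-up examination". It adds: "Unscheduled visit data will not be used". One exception readmits withdrawal and unscheduled values. It opens "For the criteria of potentially clinically significant laboratory test values, vital signs, body weight, and ECG and the categorical analysis" and goes on to the QTcF intervals. DIEPSS is not in it.

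**The concern.** The protocol asks for a rating when a subject has extrapyramidal symptoms that the investigator judges to need a drug. The SAP then summarises the scale only at fixed visits and sets unscheduled ratings aside. For a subject treated between visits, CT-14 omits the score recorded at the decision to treat. It includes the next scheduled score, taken after the drug was started, as an ordinary value. A subject who withdraws loses the withdrawal rating from CT-14 as well.

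DIEPSS is the trial's rating scale for extrapyramidal symptoms and a named safety endpoint, summarised by meal condition. If one meal condition led to more treated symptoms, the scale summary would be pulled towards smaller changes in those subjects, and nothing in the table would show it.

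**Working it through.** The plan states no figure on this point, so there is none to reproduce. The check has four steps.

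**1. Follow one rating through the rules.** A subject develops symptoms between visits and is rated under Protocol 6.5.2.
- The rating is not tied to a visit in Table 1.3-1, so it is unscheduled.
- SAP 3.4 excludes unscheduled data, and the exception does not cover DIEPSS.
- SAP 9.7.2 and CT-14 have no other route for it.
- No rule sets aside or marks the scheduled scores that follow.

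**2. How much post-dose time do the scheduled ratings cover?** Period 1 of Table 1.3-1 shows post-dose DIEPSS at 48, 168 and 312 h. The Period 2 columns are displaced in the text available. The windows in Table 1.3-2 are ±2, ±4 and ±24 h.
- Hours inside a window: 4 + 8 + 48 = 60.
- Share of the first 312 + 24 = 336 h: 60/336 = 18%.
- Share of the first 168 h: (4 + 4)/168 = 5%.
- Gaps between scheduled ratings: 168 − 48 = 120 h and 312 − 168 = 144 h.

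If drug starts were equally likely at any hour, 276/336 = 82% of these ratings would fall outside every window. That uniformity is an assumption; the documents give no timing of symptoms.

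Two details add to the gap. SAP 10.3 lets an in-window unscheduled PK sample stand in for a missing scheduled one, but no such rule exists for DIEPSS. The requirement in 6.5.2 also runs through the washout, where the table shows no scheduled DIEPSS between Period 1 Day 14 and the Period 2 baseline.

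**3. Illustrate the size.** Inputs: n = 36 planned completers (Protocol 4.1, SAP 3.1). Assumed: k subjects start a drug between visits, each having risen by a points before treatment and standing b points above baseline at the next visit. Their contribution to the mean change is k·b/n in CT-14 and k·a/n with the pre-medication rating. The hidden part is k·(a − b)/n. With a = 4 and b = 1:

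| k | In CT-14 (k × 1/36) | With pre-medication rating (k × 4/36) | Hidden (k × 3/36) |
|---|---|---|---|
| 1 | 0.03 | 0.11 | 0.08 |
| 2 | 0.06 | 0.22 | 0.17 |
| 4 | 0.11 | 0.44 | 0.33 |

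For any a from 3 to 6 and b from 0 to 2, the hidden part per affected subject runs from (3 − 2)/36 = 0.03 to (6 − 0)/36 = 0.17. The documents give neither an event rate nor typical DIEPSS changes.

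**4. Compare with the SAP's other safety measures.** Laboratory, vital-sign, ECG and weight data each get a count of subjects in whom any value up to the next dose meets a criterion (SAP 9.3, 9.4, 9.6, 9.7.1). C-SSRS has emergence and worsening categories (SAP 9.7.3). CGI-S and CGI-I have listings of subjects who worsened (CT-16.1, CT-16.2). DIEPSS has time-point statistics only.

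**The case against.** The strongest reply is that treated symptoms are visible elsewhere.
- **Adverse events.** Symptoms that arise or worsen after dosing and need a drug should be recorded as adverse events. SAP 9.2 tabulates these by term and severity, taking the most severe occurrence per period, and SAP 9 runs the analysis by meal condition.
- **Medication.** SAP 7.4 and CT-4.1 count users of each drug class from dosing to Day 14 by meal condition. Protocol 6.5.2 bars prophylactic use, so antiparkinsonian or valbenazine use there largely marks treated symptoms.
- **Listings.** PDATA-10 lists individual DIEPSS data.

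This stands, and it limits the point. A reader might infer that a meal condition causing more treated symptoms would look the same as one causing none. The documents do not support that for the safety report as a whole. These outputs do not, however, give a scale-based comparison by meal condition, and CT-4.1 does not count a drug used only between Day 14 and the next dose.

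Three further replies are fair in part.
- SAP 7.2 defines descriptive statistics to include minimum, median and maximum, so CT-14 is more than means. Each maximum is taken across subjects at one visit, though, and cannot recover an excluded rating.
- A reader might infer that the pre-medication rating is the untreated peak. Nothing guarantees that it is the highest score, and before a dose increase the subject is already on the drug. The 12-hour rule also softens the treatment effect on later scores without making them untreated.
- No test of DIEPSS between meal conditions is planned, so the issue is a misleading description and not a biased test.

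**Conclusion.** The point holds as a defect in one secondary, descriptive safety summary. A required pre-medication rating that does not coincide with a scheduled visit is left out of CT-14, and later scores taken after the drug was started enter unflagged. The DIEPSS summary by meal condition can therefore understate extrapyramidal severity in treated subjects.

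The size is unknown. The figures of 82% and of 0.03 to 0.17 points per affected subject rest on an assumed uniform timing and on assumed scores; they show how the mechanism works and are not estimates. The conclusion rests on reading the 6.5.2 rating as unscheduled when it falls between visits, which follows from SAP 3.4 and Table 1.3-1. The rating leaves the summary, not the data, provided that it is entered in the eCRF. The primary pharmacokinetic analysis is untouched.

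**What to change.** Change the SAP as follows.
1. In SAP 3.4, add DIEPSS to the exception that readmits withdrawal and unscheduled values.
2. In SAP 9.7.2 and CT-14, add by meal condition each subject's maximum post-dose DIEPSS total and its change from the period baseline. Use scheduled, withdrawal and 6.5.2 pre-medication ratings up to the next IMP dose.
3. Add the number and proportion of subjects whose total score increased.
4. Flag scores taken after an antiparkinsonian drug or valbenazine was started or increased in that period.

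The cost is SAP wording and a few table rows. Medication start and end dates and doses are already recorded (Protocol 6.5). One thing needs confirming: Protocol 8.7.6.2 sends DIEPSS results to the eCRF but refers only to Table 1.3-1 for timing, so the sponsor should check that the eCRF captures the 6.5.2 rating with its date and time. No clinical procedure changes.
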